5.3.2. Analysis Method

Exploratory analysis will be done on the PPE analysis set including only baseline seronegative subjects. The analysis will focus on the Omicron variant, as this is presumed to be the dominant variant during the observation period.

Analysis will be performed if there are at least 6 cases available for the analysis of interest.

i) Calendar-Based Time Scale Method:

For the exploratory efficacy endpoints, follow-up time will be expressed on a calendar time scale, and is defined as time since study start (i.e., 08 August 2021) to adjust for changing incidence over time. Follow-up time will begin on the date of administration of the first dose of Janssen COVID-19 vaccine (within study COV2008), expressed on a calendar time scale as time since study start,

although follow-up time and events occurring within 14 days post vaccination with first dose of Janssen COVID-19 vaccine will be ignored.

The follow-up time is the time to first occurrence of moderate to severe disease, with an onset at any time at least 14 days post vaccination of previously received Janssen COVID-19 vaccine. An individual will be censored at i) the date of receipt of another authorized/approved COVID-19 vaccine, including the Janssen COVID-19 vaccine if received outside of the study, ii) the date of study discontinuation, or iii) the last available date, whichever occurred first.

Vaccine efficacy will be summarized by relative vaccine efficacy measures and the associated 95% confidence intervals (CI) using time-dependent Cox Proportional hazards models , stratified by the following factors to account for i) changing incidence over calendar time, ii) potential confounding by age [18 - <60 years (as reference category), ≥ 60 years], co-morbidities [Y/N (as a reference category)] and geographical region in which the site is located (cf. Section 5.4.1).

One model will be fit estimating VE under the assumption of constant relative vaccine efficacy (Fintzi et al, 2020), comparing:

- Within each Cohort, from higher dose levels (i.e. Ad26.COV2.S 5×10^{10} vp and 2.5×10^{10} vp) to lower dose level (Ad26.COV2.S 1×10^{10} vp).
- Heterologous booster (Cohort 2) to homologous booster (Cohort 1) vaccination at same dose level.

Models that do not converge will be omitted and reported as non-convergent. The method for tabulating relative VE and 95% CI will be detailed in DPS.

Estimand 2:

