5.6. Safety Analyses

All safety analyses will be based on the FAS based on actual intervention received, unless otherwise specified.

All continuous safety variables, descriptive statistics by intervention group will include the N, mean, standard deviation, median, minimum, and maximum. Categorical variables will be summarized by vaccination group using frequency counts and percentages. All safety data summary will be presented by Cohort where Cohort 1 includes participants who received Ad26.COV2.S as primary vaccination; and Cohort 2 includes those who received BNT162b2 as primary vaccination, unless specified otherwise. In addition, selected safety results will be presented in the same output with both cohorts.

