5.8.2. Planned Analysis

The primary and final analyses of Cohort 1 may be performed before the analyses of Cohort 2.

The primary analysis of safety and immunogenicity in Cohort 1 or Cohort 2 will be performed when all evaluable participants in the respective cohort have completed the visit that takes place 28 days after study vaccination or discontinued earlier. The analysis will include immunogenicity data (VNA, S-ELISA, N-serology) for all evaluable participants through Day 15, and all available safety data. The sponsor will be unblinded for the respective cohort at the time of this primary analysis, but the blind will be maintained at the participant and study site level up to study end.

The final analysis in Cohort 1 or Cohort 2 will be performed when all included participants in the respective cohort have completed their last visit or discontinued earlier.

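### The between-cohort rVE model has no term for time since booster, so a difference in booster dates between cohorts could pass for a regimen effect

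*SAP*

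**What the plan says.** Supplemental SAP Section 5.3.2 gives one method. The time scale is calendar time, "defined as time since study start (i.e., 08 August 2021) to adjust for changing incidence over time". Participants enter at their in-study booster: "Follow-up time will begin on the date of administration of the first dose of Janssen COVID-19 vaccine (within study COV2008"; the first 14 days are ignored. Estimation is "using time-dependent Cox Proportional hazards models", stratified for changing incidence and for "potential confounding by age", comorbidity and region. The effect is held constant: "One model will be fit estimating VE under the assumption of constant relative vaccine efficacy". One of the two listed contrasts is "Heterologous booster (Cohort 2) to homologous booster (Cohort 1) vaccination at same dose level". The method is repeated for Estimands 2 to 5. The interim text (Section 5.5) keeps the calendar scale and adds only optional stratification by age, comorbidity, site or region.

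Neither section names a term for time since booster or booster date, or a sensitivity analysis on a time-since-booster scale. The Kaplan-Meier plots by cohort (Section 5.3.3) are descriptive.

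Main SAP Section 5.6 defines the cohorts: "Cohort 1 includes participants who received Ad26.COV2.S as primary vaccination; and Cohort 2 includes those who received BNT162b2 as primary vaccination". On timing, main SAP Section 5.8.2 says only: "The primary and final analyses of Cohort 1 may be performed before the analyses of Cohort 2".

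**The concern.** A calendar-time risk set compares people on the same date. That deals with changing incidence, but it does not align people by time since booster. Dose groups enrolled and randomised together within a cohort should have similar booster dates, so their contrasts are largely protected. Between cohorts nothing in the design or the model does this, and follow-up covers the whole study (supplemental SAP Section 5.1), long enough for waning to act.

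Heterologous versus homologous rVE is the first objective of the supplemental SAP and accounts for 15 estimands (three dose levels for each of five endpoints). A reader would take a non-zero estimate as a property of the regimen when part of it could be a difference in booster dates.

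**Working it through.** The SAP gives no expected lag, waning rate, event count or rVE for this contrast, so there is no planned figure to reproduce. The check asks what the planned model returns when the true rVE is zero.

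**Inputs.** From Section 5.3.2: calendar scale, delayed entry at booster, constant effect. Assumed: the cohorts' booster dates differ by L months, and the hazard after boosting is multiplied by m every 6 months, equally in both cohorts.

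**Step 1, closed form.** For a person boosted at b, the hazard on date t is λ(t)·exp(g(t − b)), with g = ln(m)/6. The factor λ(t)·exp(gt) is common to everyone on that date and goes into the baseline. What remains gives HR (later/earlier cohort) = exp(−gL) and spurious rVE = 100·(1 − exp(−gL)). Example with m = 2, L = 2: g = 0.6931/6 = 0.1155; exp(−0.231) = 0.794; rVE = 20.6%.

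| m per 6 months | L = 0 | L = 1 | L = 2 | L = 3 |
|---|---|---|---|---|
| 1 (no waning) | 0 | 0 | 0 | 0 |
| 1.25 | 0 | 3.7% | 7.2% | 10.6% |
| 1.5 | 0 | 6.5% | 12.6% | 18.4% |
| 2 | 0 | 10.9% | 20.6% | 29.3% |
| 3 | 0 | 16.7% | 30.7% | 42.3% |

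**Step 2, simulation.** A left-truncated calendar-time Cox model (300 per cohort, 1.5-month enrolment, one epidemic wave, 40 runs) gave −0.4, 11.8, 19.4 and 30.2% for m = 2, and −0.9, 18.1, 31.1 and 40.6% for m = 3. This agrees with Step 1.

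**Step 3, bounded waning.** Step 1 lets waning run without limit, which overstates the bias over long follow-up. Suppose the hazard relative to no booster rises from 0.5 to 0.8 over 4 months: k = ln(1.6)/4 = 0.1175 per month. Unchecked, it passes 1 at ln(2)/0.1175 = 5.9 months and reaches 0.5 × 1.6³ = 2.05 at 12 months. Holding it at 0.8 after month 4 gives these HRs (later/earlier):

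| Wave peak | 30-day lag | 60-day lag | 90-day lag |
|---|---|---|---|
| Day 120 | 0.90 | 0.85 | 0.80 |
| Day 200 | 0.96 | 0.91 | 0.84 |
| Day 300 | 1.02 | 0.98 | 0.96 |

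A second simulation with waning held after month 4 gave 0.95-0.97, 0.85-0.95 and 0.82-0.87. The bias therefore runs from almost nil, when cases fall after waning has levelled off, to about 20%.

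**Step 4, adding time since booster.** At a fixed date, a linear term in time since booster is equivalent to one in booster date. With m = 2 and lags of 1, 2 and 3 months:

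| Lag (months) | Adjusted rVE (truth 0) | SD of log HR, unadjusted → adjusted | Ratio |
|---|---|---|---|
| 1 | +2.1% | 0.12 → 0.18 | 1.5 |
| 2 | −1.1% | 0.09 → 0.25 | 2.8 |
| 3 | −2.8% | 0.11 → 0.38 | 3.5 |

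Root mean square error of the unadjusted log HR, √((gL)² + SD²):
- Lag 1: √(0.116² + 0.12²) = 0.17
- Lag 2: √(0.231² + 0.09²) = 0.25
- Lag 3: √(0.347² + 0.11²) = 0.36

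The adjusted model has almost no bias, so its error is about its SD: 0.18, 0.25 and 0.38. Adjustment trades bias for variance without reducing total error. At lags of 2 and 3 months the simulated enrolment windows (0-1.5 against 2-3.5 or 3-4.5 months) do not overlap, so the adjusted estimate leans on the assumed shape of waning.

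**Step 5, coarse bands.** Bands of 14-60, 61-120 and >120 days, under unbounded waning with a day-200 wave, moved the HRs at 30, 60 and 90 days only from 0.89/0.78/0.71 to 0.92/0.82/0.76. With a day-300 wave the HRs hardly moved (0.88/0.77/0.72 to 0.89/0.78/0.72). The open last band holds most of a one-year follow-up.

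**Step 6, sign.** The estimand tables in Section 5.3.1.1 take Cohort 1 over Cohort 2; Section 5.3.2 describes Cohort 2 against Cohort 1. If Cohort 2 were the later cohort (m = 2), the second reading gives +10.9, +20.6 and +29.3%. The first gives 100·(1 − 1/0.891) = −12%, 100·(1 − 1/0.794) = −26% and 100·(1 − 1/0.707) = −41%.

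**The case against.** The strongest objection is that no lag is documented, and it stands. A reader might infer from main SAP Section 5.8.2 that Cohort 1 was boosted first, and hence that the model favours the heterologous regimen. The documents do not support that. The sentence is permissive and concerns when analyses are run. Cohort 2 also depends on about 300 external serum samples, which could by itself separate the analyses. Main SAP Section 5.8.1 plans safety outputs at the Cohort 1 interim for all available participants in both cohorts, which suggests at least partly overlapping enrolment, and Section 5.3.2 uses one study start. With no lag, or no waning, there is no bias.

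It is also fair to say that the analysis is exploratory with no decision rule, and that the adjusted model is costly. Section 5.3.2 allows a model with as few as 6 cases, too few to support extra parameters. This argues against replacing the main model.

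Two defences fail. Calling the Cox model time-dependent does not help, because no time-varying term is named and the effect is explicitly constant. The calendar scale adjusts for incidence, not for waning.

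**Conclusion.** The point holds in conditional form. As planned, Estimands x.3 to x.5 cannot separate regimen from time since booster. If booster dates differ and protection wanes, the later-boosted cohort looks better with identical regimens. Under the assumed lags of 1-3 months the spurious rVE is roughly 5-30% in most settings examined, near nil when the wave comes after waning has levelled off, and above 40% only with a hazard tripling every 6 months at a 3-month lag. It is nil at zero lag. These figures rest on assumed lags, waning and epidemic shape; the documents supply none of them, so neither the size nor the favoured cohort can be stated. The finding does not extend to the within-cohort dose contrasts.

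**What to change.** 1. Tabulate booster dates by cohort and dose group, and show how far they overlap.
2. For the between-cohort contrasts only, pre-specify a sensitivity analysis that keeps the calendar scale and adds time since booster as a time-varying covariate common to both cohorts. Make it continuous, or finely banded with no open class above 120 days. Run it when the number of cases supports the extra parameter, and state that number in advance.
3. State that the contrast is poorly identified, and is not to be read as a regimen effect, if booster dates barely overlap or if the main and sensitivity estimates diverge.
4. Use one direction for the between-cohort hazard ratio in Sections 5.3.1.1 and 5.3.2 and in the repeated estimand tables.

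The cost is SAP wording, one table and one derived variable; booster dates are already needed to define entry into follow-up. The downside is one extra analysis with clearly wider intervals: the SD of the log HR is about two to three times larger at lags of 2-3 months (2.8 and 3.5 times in the setting shown, from 40 runs each). With few cases it may not be estimable, and that should be reported.

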4. POPULATIONS (ANALYSIS SETS) FOR ANALYSIS

The analysis set used for the exploratory analyses are described in [Table 2](#).

Table 2: Analysis Sets

Analysis Sets	Description
Per Protocol Efficacy Analysis Set (PPE)	All vaccinated participants who are SARS-CoV-2 seronegative at baseline and who have no major protocol deviations (listed in Appendix 4 of main SAP) expected to impact the efficacy outcomes.

All analyses of exploratory rVE endpoints will be performed based on PPE Analysis Set.

Follow-up time and COVID-19 cases within 14 days after booster vaccination are excluded from the analysis.

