5.2.5. Asymptomatic or Undetected SARS-COV-2 Infection

5.2.5.1. Definition

If a participant does not fulfil the criteria for suspected COVID-19 based on signs and symptoms which would classify them as mild, moderate, or severe by the definitions,

AND

has a SARS-CoV-2 positive RT-PCR or molecular test result from any available respiratory tract sample (e.g., nasal swab sample, sputum sample, throat swab sample, saliva sample) or other sample

OR

determined by seropositivity for the SARS-CoV-2 N protein,

then, the participant will be considered to have experienced asymptomatic or undetected COVID-19.

A positive RT-PCR for SARS-CoV-2 will need to be captured in the eCRF.

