5.2.5.2. Classification

Asymptomatic infections or undetected cases will be classified using a similar algorithmic approach. Cases will then be reviewed and classified by the CSAC.

Relevant definitions for programmed algorithm

Identification of potential asymptomatic SARS-CoV-2 infections via PCR: Cases with a positive PCR will be reviewed for the presence of signs and/or symptoms of COVID-19 employing the definitions of onset and resolution of section 5.2.2. In the absence of signs and/or symptoms, the case will be classified per algorithm as asymptomatic.

Identification of potential asymptomatic or undetected SARS-CoV-2 infections through seroconversion:

- **SARS-CoV-2 seroconversion by N-serology with onset Day >14** is based on the available data from Day 71, Month 6. If positive at any timepoint while the subject was seronegative at baseline (and at Day 15 for the PPE analysis after day 14), a subject is considered to have seroconverted. If Day 14 is missing or not available, the subject is considered to be negative on that day.
- **SARS-CoV-2 seroconversion by N-serology from Day 1 to Day 14**, is based on the available data on day 14. If positive at day 14 while the subject was seronegative at baseline or missing, a subject is considered to have seroconverted between day 1 and day 14.
- **A seroconverted participant** is a subject with serological conversion without an earlier SARS-CoV-2 positive RT-PCR or molecular test result from any available respiratory tract sample.

Upon algorithmic classification, cases will be evaluated as being an "Asymptomatic SARS-CoV-2 infection" by the Clinical Severity Adjudication Committee as follows:

- Asymptomatic SARS-CoV-2 infections or seroconverted participants as assigned via the programmed algorithm will be reviewed for the presence of possible COVID-19 signs and symptoms from baseline up to 7 days prior to the first positive PCR or up to the day of the first positive serology test.
- If no presence of signs/symptoms, the algorithm will be accepted and no further review by the CSAC and the case classified as Asymptomatic SARS-CoV-2 infection.
- If at least one sign or symptom is present, those cases will be sent to the CSAC for review for a possible undetected symptomatic COVID-19 illness.
 - If reviewed by the CSAC as asymptomatic SARS-CoV-2 infections, cases will be classified as asymptomatic infection.

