5.3. Exploratory Endpoint(s) Analysis

5.3.1. Definition of Endpoints and Estimands

5.3.1.1. Exploratory endpoint(s)

The exploratory endpoint(s) is defined as a COVID-19 case meeting case definitions, as defined in Sections 5.2.4 and 5.2.5, with onset at least 14 days post last vaccination.

Estimand 1:

What is the relative vaccine efficacy against moderate to severe/critical COVID-19 of Ad26.COV2.S booster vaccination at different dose levels within and between cohorts in adults ≥ 18 years with or without comorbidities associated with increased risk of progression to severe COVID-19?

Population: Adults ≥ 18 years with or without comorbidities associated with increased risk of progression to severe COVID-19 cases and who previously received primary vaccination with Ad26.COV2.S or BNT162b2 and subsequently received Ad26.COV2.S boost on the study.

Endpoint: Molecularly confirmed symptomatic moderate to severe/critical COVID-19 Omicron infections with onset ≥ 14 days after last study vaccination.

Intercurrent Events: Other COVID-19 vaccines.

Data handling for estimators: Cases will be counted from the day after last Ad26.COV2.S vaccination until and including the last available timepoint in the database. Participants with a SARS-CoV-2 infection (symptomatic or asymptomatic) prior to 14 days post last study vaccination will be excluded from the risk set.

A subject will be censored:

- If no event of interest to the analysis was experienced during the considered observation period
- On the date of receipt of another authorized/approved COVID-19 vaccine outside of the study, the date of study discontinuation or the last available date (data lock point), whichever occurred first.

The above defined Estimand approach will be used for following interventions and summary measures:

Estimand	Interventions	Summary Measures ¹
Within each Cohort: (Cohort 1 and 2 separately)		
Estimand 1.1	Ad26.COV2.S 5×10^{10} vp and Ad26.COV2.S 1×10^{10} vp	Relative VE = 100 x (1-hazard ratio of Ad26.COV2.S 5×10^{10} vp / Ad26.COV2.S 1×10^{10} vp)%
Estimand 1.2	Ad26.COV2.S 2.5×10^{10} vp and Ad26.COV2.S 1×10^{10} vp	Relative VE = 100 x (1-hazard ratio of incidence Ad26.COV2.S 2.5×10^{10} vp / Ad26.COV2.S 1×10^{10} vp)%
Between Cohorts:		
Estimand 1.3	Ad26.COV2.S 5×10^{10} vp (Cohort 1) and Ad26.COV2.S 5×10^{10} vp (Cohort 2)	Relative VE = 100 x (1-hazard ratio of Cohort 1 Ad26.COV2.S 5×10^{10} vp / Cohort 2 Ad26.COV2.S 5×10^{10} vp)%

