Estimand 4.2	Ad26.COV2.S 2.5×10^{10} vp and Ad26.COV2.S 1×10^{10} vp	Relative VE = $100 \times (1 - \text{hazard ratio of incidence Ad26.COV2.S } 2.5 \times 10^{10} \text{ vp} / \text{Ad26.COV2.S } 1 \times 10^{10} \text{ vp})\%$
Between Cohorts:		
Estimand 4.3	Ad26.COV2.S 5×10^{10} vp (Cohort 1) and Ad26.COV2.S 5×10^{10} vp (Cohort 2)	Relative VE = $100 \times (1 - \text{hazard ratio of Cohort 1 Ad26.COV2.S } 5 \times 10^{10} \text{ vp} / \text{Cohort 2 Ad26.COV2.S } 5 \times 10^{10} \text{ vp})\%$
Estimand 4.4	Ad26.COV2.S 2.5×10^{10} vp (Cohort 1) and Ad26.COV2.S 2.5×10^{10} vp (Cohort 2)	Relative VE = $100 \times (1 - \text{hazard ratio of Cohort 1 Ad26.COV2.S } 2.5 \times 10^{10} \text{ vp} / \text{Cohort 2 Ad26.COV2.S } 2.5 \times 10^{10} \text{ vp})\%$
Estimand 4.5	Ad26.COV2.S 1×10^{10} vp (Cohort 1) and Ad26.COV2.S 1×10^{10} vp (Cohort 2)	Relative VE = $100 \times (1 - \text{hazard ratio of Cohort 1 Ad26.COV2.S } 1 \times 10^{10} \text{ vp} / \text{Cohort 2 Ad26.COV2.S } 1 \times 10^{10} \text{ vp})\%$

¹Relative VE and associated 95% CI will be calculated from Cox Proportional hazards model.

Analysis method will be repeated as explained in Section 5.3.2.

Estimand 5:

What is the relative vaccine efficacy against asymptomatic/undetected COVID-19 of Ad26.COV2.S booster vaccination at different dose levels within and between cohorts in adults ≥ 18 years with or without comorbidities associated with increased risk of progression to severe COVID-19?

Population: Adults ≥ 18 years with or without comorbidities associated with increased risk of progression to severe COVID-19 cases and who previously received primary vaccination with Ad26.COV2.S or BNT162b2 and subsequently received Ad26.COV2.S boost on the study.

Endpoint: Asymptomatic/undetected COVID-19 Omicron infections with onset ≥ 14 days after last study vaccination.

Intercurrent Events: Other COVID-19 vaccines

Data handling for estimators: Cases will be counted from the day after last Ad26.COV2.S vaccination until and including the last available timepoint in the database. Participants with a SARS-CoV-2 infection (asymptomatic/undetected) prior to 14 days post last study vaccination will be excluded from the risk set.

A subject will be censored:

- If no event of interest to the analysis was experienced during the considered observation period

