- On the date of receipt of another authorized/approved COVID-19 vaccine outside of the study, the date of study discontinuation or the last available date (data lock point), whichever occurred first.

The above defined Estimand approach will be used for following interventions and summary measures:

Estimand	Interventions	Summary Measures ¹
Within each Cohort: (Cohort 1 and 2 separately)		
Estimand 5.1	Ad26.COV2.S 5×10^{10} vp and Ad26.COV2.S 1×10^{10} vp	Relative VE = $100 \times (1 - \text{hazard ratio of Ad26.COV2.S } 5 \times 10^{10} \text{ vp} / \text{Ad26.COV2.S } 1 \times 10^{10} \text{ vp})\%$
Estimand 5.2	Ad26.COV2.S 2.5×10^{10} vp and Ad26.COV2.S 1×10^{10} vp	Relative VE = $100 \times (1 - \text{hazard ratio of incidence Ad26.COV2.S } 2.5 \times 10^{10} \text{ vp} / \text{Ad26.COV2.S } 1 \times 10^{10} \text{ vp})\%$
Between Cohorts:		
Estimand 5.3	Ad26.COV2.S 5×10^{10} vp (Cohort 1) and Ad26.COV2.S 5×10^{10} vp (Cohort 2)	Relative VE = $100 \times (1 - \text{hazard ratio of Cohort 1 Ad26.COV2.S } 5 \times 10^{10} \text{ vp} / \text{Cohort 2 Ad26.COV2.S } 5 \times 10^{10} \text{ vp})\%$

Estimand	Interventions	Summary Measures ¹
Estimand 5.4	Ad26.COV2.S 2.5×10^{10} vp (Cohort 1) and Ad26.COV2.S 2.5×10^{10} vp (Cohort 2)	Relative VE = $100 \times (1 - \text{hazard ratio of Cohort 1 Ad26.COV2.S } 2.5 \times 10^{10} \text{ vp} / \text{Cohort 2 Ad26.COV2.S } 2.5 \times 10^{10} \text{ vp})\%$
Estimand 5.5	Ad26.COV2.S 1×10^{10} vp (Cohort 1) and Ad26.COV2.S 1×10^{10} vp (Cohort 2)	Relative VE = $100 \times (1 - \text{hazard ratio of Cohort 1 Ad26.COV2.S } 1 \times 10^{10} \text{ vp} / \text{Cohort 2 Ad26.COV2.S } 1 \times 10^{10} \text{ vp})\%$

¹Relative VE and associated 95% CI will be calculated from Cox Proportional hazards model.

Analysis method will be repeated as explained in Section [5.3.2](#).

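### Estimand 5 keeps participants with a symptomatic infection at risk for asymptomatic infection although an earlier positive PCR rules out a seroconversion event; rVE shifts if symptomatic risk differs between arms

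*SAP*

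**What the plan says.** All references are to the supplemental SAP unless stated.

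- **Endpoint (5.3.2, Estimand 5).** "Asymptomatic/undetected COVID-19 Omicron infections with onset ≥ 14 days after last study vaccination".
- **Infections before Day 14, Estimand 5.** "Participants with a SARS-CoV-2 infection (asymptomatic/undetected) prior to 14 days post last study vaccination will be excluded from the risk set".
- **Infections before Day 14, Estimand 1 (5.3.1.1; same in Estimands 2 and 3).** "Participants with a SARS-CoV-2 infection (symptomatic or asymptomatic) prior to 14 days post last study vaccination will be excluded from the risk set".
- **Censoring, Estimand 5.** A participant without the event is censored "On the date of receipt of another authorized/approved COVID-19 vaccine outside of the study, the date of study discontinuation or the last available date", whichever came first. The general method at the start of 5.3.2, which Estimand 5 repeats, has in substance the same list. Neither mentions infection.
- **Intercurrent events, Estimand 5.** "Intercurrent Events: Other COVID-19 vaccines". Nothing else is named.
- **Seroconversion (5.2.5.2).** A seroconverted participant "is a subject with serological conversion without an earlier SARS-CoV-2 positive RT-PCR or molecular test result from any available respiratory tract sample".
- **PCR route to the same endpoint (5.2.5.1).** A participant without qualifying symptoms also counts if he or she "has a SARS-CoV-2 positive RT-PCR or molecular test result from any available respiratory tract sample".
- **General 14-day rule (section 4).** "Follow-up time and COVID-19 cases within 14 days after booster vaccination are excluded from the analysis".

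**The concern.** The risk set and the event definition do not match. Once a participant has had a PCR-positive symptomatic infection, 5.2.5.2 closes the seroconversion route, but Estimand 5 goes on counting that participant as at risk. This happens in two places: before Day 14, because the exclusion names only asymptomatic/undetected infections, and after Day 14, because the censoring list has no infection rule.

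Symptomatic infection is an outcome that the boosters may affect differently; Estimands 1 to 4 compare the arms on it. If one arm has more symptomatic infections, it gathers more person-time in which a seroconversion cannot be counted, and its asymptomatic hazard looks lower than it is. The arm with fewer symptomatic infections then looks worse against asymptomatic infection than its cause-specific hazard ratio would show.

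**Working it through.** **1. Does another rule close the gap?** The rule in section 4 drops early time and early cases; it does not say that a participant with an early symptomatic infection leaves later follow-up. The PPE set removes baseline seropositives and major protocol deviations, not symptomatic cases after the booster. The general method in 5.3.2 has no infection rule. So the gap stands, and after Day 14 it is unambiguous.

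**2. Inputs for the size.** The SAP gives no attack rate, event count or power for Estimand 5, so there is no figure to reproduce. Assumed: two equal arms, follow-up scaled to 1, constant cause-specific hazards, asymptomatic risk 20% in the arm with more symptomatic infections, and symptomatic risks as in the table. Each risk is stated as if it were the only type of infection. From the SAP: symptomatic cases stay in the risk set, and rVE = 100 × (1 − Cox hazard ratio).

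**3. Formulas.** Hazard = −ln(1 − risk). With asymptomatic hazard *a* and symptomatic hazard *s* in an arm, and no events after a symptomatic infection:

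- event density: n(t) = a·exp(−(a+s)t)
- proportion with the event by t: F(t) = [a/(a+s)]·[1 − exp(−(a+s)t)]
- risk set as the SAP writes it: R(t) = 1 − F(t)

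The limiting Cox log hazard ratio β solves ∫{n₁ − (n₀+n₁)·e^β R₁/(e^β R₁ + R₀)}dt = 0, where arm 1 has fewer symptomatic infections. For the reinfection variant, a hazard of 0.3*a* is kept after a symptomatic infection.

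**4. Hand check, 30 v 20% symptomatic, true rVE 0.** a = −ln 0.8 = 0.2231 in both arms; s₀ = −ln 0.7 = 0.3567; s₁ = −ln 0.8 = 0.2231.

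- F₀ = (0.2231/0.5798) × (1 − 0.8 × 0.7) = 0.1693
- F₁ = (0.2231/0.4463) × (1 − 0.8 × 0.8) = 0.1800
- ratio of cumulative hazards as the SAP counts them: ln(1 − 0.1800)/ln(1 − 0.1693) = 0.1985/0.1855 = 1.070

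That is an rVE of about −7.0%. The score equation gives −6.7%; the two differ slightly because the apparent hazards are not proportional.

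**5. Results.**

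| Symptomatic risk, arm 0 v arm 1 | True rVE 0: as written | True rVE 0: 30% of hazard kept | True rVE 30%: as written |
|---|---|---|---|
| 30 v 30% | 0.0% | 0.0% | 29.8% |
| 5 v 2.5% | −1.3% | −0.9% | 29.0% |
| 10 v 5% | −2.8% | −1.9% | 28.0% |
| 20 v 15% | −3.1% | −2.0% | 27.7% |
| 30 v 20% | −6.7% | −4.4% | 25.1% |
| 40 v 25% | −11.2% | −7.1% | 21.9% |
| 40 v 20% | −14.8% | −9.4% | 19.4% |

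**6. Effect of censoring at the first infection.** Simulation with 100,000 per arm, 10% asymptomatic risk, 30% symptomatic risk in arm 0 and a symptomatic hazard ratio of 0.5: for a true rVE of 30% the written rule gave 22.6% and censoring gave 29.2%; for a true rVE of 0 they gave −9.2% and −0.2%.

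**The case against.** **A recognised estimand may be intended.** Keeping participants with a competing event in the risk set is what a subdistribution hazard does, and that is a legitimate measure of effect on cumulative incidence. This stands in part: the shift is a bias only relative to a cause-specific target. But the SAP names no such strategy, lists other vaccines as the only intercurrent event, and treats early infections in Estimand 5 unlike those in Estimands 1 to 3.

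**The Day 14 sentence is not the source of the figures.** A reader might infer that it is. The model has no infections before Day 14; every figure comes from the missing censoring rule. The sentence is an inconsistency whose own effect has not been sized. Section 4 can arguably be read as removing early symptomatic cases too, but it does nothing after Day 14.

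**The event is not impossible after a symptomatic infection.** Only seroconversion is ruled out; an asymptomatic PCR-positive reinfection can still count under 5.2.5.1. With 30% of the asymptomatic hazard kept, the shift falls by about a third.

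**The timing is simplified.** Section 5.2.5.2 reads seroconversion after Day 14 from the Day 71 and Month 6 samples, while the model spreads events over follow-up. The true size could move either way.

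**The shift is small against the precision.** The main SAP (5.8.1) puts 110 participants at about 33% of Cohort 1 Group 1, so about 330. Assuming 330 per arm and 20% asymptomatic risk gives 66 events per arm, SE(log HR) = √(2/66) = 0.174, and a 95% CI around rVE 0 of about −41% to 29%. The largest tabulated null shift, ln 1.148 = 0.138, is below one standard error. The analysis is also exploratory. This limits the weight of the point, but does not make the risk set agree with the event definition.

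**Censoring has its own assumption.** Symptomatic and asymptomatic infection are alternative outcomes of the same exposure. That censoring recovers the true value in step 6 follows from the model's independent hazards.

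**Conclusion.** The point holds as a mismatch between the Estimand 5 risk set and the seroconversion definition, with no stated strategy for symptomatic infection. Read as a cause-specific hazard ratio, rVE against asymptomatic infection is shifted against the arm with fewer symptomatic infections, on condition that symptomatic risk differs between the compared arms.

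A reader might go further and infer that Estimand 5 is biased against the more protective regimen whatever the data. The documents do not support that. They give no attack rates and no difference in symptomatic risk; with equal risks the shift is about nil, and at symptomatic risks of 5 to 10% it is about 1 to 3 points. Shifts of 7 to 15 points (true rVE 0) need symptomatic risks of 30 to 40% and a clear difference between arms (symptomatic hazard ratios of about 0.63 down to 0.44). All these sizes rest on constant hazards, 20% asymptomatic risk and no reinfection events. They illustrate the effect and do not predict it for this trial. The text should be corrected before the analysis, in proportion to an exploratory estimand.

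**What to change.** Three wording changes to Estimand 5 in 5.3.2:

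1. For infections before Day 14, use the Estimand 1 to 3 rule: "Participants with a SARS-CoV-2 infection (symptomatic or asymptomatic) prior to 14 days post last study vaccination will be excluded from the risk set".
2. Add to the censoring list the onset date of the first symptomatic SARS-CoV-2 infection, whether molecularly confirmed or classed by the adjudication committee as serologically confirmed COVID-19 (end of 5.2.5.2). A rule limited to molecularly confirmed cases would leave participants who have already seroconverted at risk.
3. State that the resulting rVE is based on a cause-specific hazard ratio.

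If the sponsor does intend a subdistribution hazard, the SAP should say so and name symptomatic infection as the competing event; the first change is needed either way for consistency.

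The cost is SAP text and a small programming change; onset dates are already derived and adjudicated (5.2, 5.2.2). There are two downsides. Asymptomatic reinfections after a symptomatic episode are no longer counted. And reading the estimate as the effect that would be seen without symptomatic infection would need independent censoring, which is doubtful here and should be said in the report.
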